1.2 Trial Design

This will be a phase 1a randomized, open label, multi-center study with approximately 24 subjects. All subjects will receive SOC per institutional guidelines for treatment of patients with COVID-19 infection. In addition to SOC, the brequinar group will receive brequinar 100 mg once daily for 5 days.

Subjects will have a Screening Visit followed as soon as possible with Study Day 1 (Day 1 may take place on the same day if entry criteria data are available). Subjects will be followed through Day 15, with mortality assessed via a phone call/other digital media acceptable to institution on Day 29.

Confidential Document

	CCB-CRISIS-01 Statistical Analysis Plan	Revision No. 1.0
	Document Date: 17-Dec-2020	Page 7 of 17

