1.2.1 Number of Subjects and Randomization

Subjects who meet all the inclusion and none of the exclusion criteria will be enrolled in the study until approximately 24 subjects have completed the study. Subjects will be randomized to either SOC or SOC plus brequinar or in a 1:2: ratio (approximately 8 subjects assigned to SOC alone and approximately 16 subjects on SOC plus brequinar).

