2.5.3 Exploratory Efficacy Analyses

Changes from baseline will be summarized by treatment:

- Viral load (nasopharyngeal) (Days 3, 5, 7, and 15)
- Inflammatory markers (Days 3, 5, 7, and 15)
- DHO levels (Days 3, 5, 7, and 15)
- Brequinar concentration levels (Days 3, 5 and 7)

For inflammatory markers (including pro-inflammatory cytokines), results from both local and central laboratories will be combined, where the local test result will be normalized where necessary. (See [Section 3.2](#) for normalization method).

Viral culture results will be provided in data listings only.

Confidential Document

	CCB-CRISIS-01 Statistical Analysis Plan	Revision No. 1.0
	Document Date: 17-Dec-2020	Page 10 of 17

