3. DATA HANDLING

3.1 Baseline and Study Visits

Study Day 1 will be the day of randomization.

The summary of hospitalization status will be based on the Study Day (derived relative to the day of randomization).

For the summary of inflammatory markers, Baseline will be the last assessment prior to dosing (SOC plus brequinar group) or last assessment on or prior to Study Day 1 (SOC group). Post-baseline timepoints will be based on the Study Day (derived relative to the day of randomization), where Day 15 includes a 4-day window (Study Day 11-19). If there are multiple results on the same day, the earliest result will be used.

For all other summaries, post-baseline timepoints will use the visit as recorded on the case report form, and Baseline will be the last non-missing value prior to randomization, including unscheduled assessments. Otherwise, unscheduled data will not be used in the analyses, but will be presented in the listings.

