3.3 Missing Data and Data Conventions

No imputation is planned for missing data.

The follow conventions will be used for data handling:

- If SARS-Cov-2 is “not detected” in specimen, the test result will be set to 0 for analysis.
- For DHO and brequinar concentration levels, samples below the lower limit of quantitation (LLOQ) will be set to half of the LLOQ value for the summary tables (LLOQ of DHO is 5 ng/mL, LLOQ of concentration level is 5 mcg/mL).
- If a laboratory test result is reported as “< xxx” or “> xxx”, the value of “xxx” will be used for analysis.
- If a medication or procedure has an incomplete start date, it is assumed to have started prior to randomization, unless the month and year are after randomization.
- If a medication or procedure is not checked as ongoing and has an incomplete stop date, it is assumed to have stopped after randomization, unless the month and year are prior to randomization.

Confidential Document

	CCB-CRISIS-01 Statistical Analysis Plan	Revision No. 1.0
	Document Date: 17-Dec-2020	Page 14 of 17

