n	xx	xx	xx	xx
Mean (SE)	xx.x (xx.xx)	xx.x (xx.xx)	xx.x (xx.xx)	xx.x (xx.xx)
Median	xx.x	xx.x	xx.x	xx.x
Q1, Q3	xx.x, xx.x	xx.x, xx.x	xx.x, xx.x	xx.x, xx.x
Min, Max	xx, xx	xx, xx	xx, xx	xx, xx
etc.				
Source: Listing 16.x.x.x				

Programming note: Include Day 3, 5, 7, 15.

Clear Creek Bio., Inc.: Protocol CCB-CRISIS-01

Table 14.2.8

Summary of Change from Baseline in Brequinar Concentration Level (mcg/mL)
by Treatment and Visit
Intent-to-Treat Population

Visit	SOC + Brequinar (N=xx)		SOC (N=xx)	
	Visit	Change from Baseline	Visit	Change from Baseline
Baseline				
n	xx		xx	
Mean (SE)	xx.x (xx.xx)		xx.x (xx.xx)	
Median	xx.x		xx.x	
Q1, Q3	xx.x, xx.x		xx.x, xx.x	
Min, Max	xx, xx		xx, xx	
Day 3				
n	xx	xx	xx	xx
Mean (SE)	xx.x (xx.xx)	xx.x (xx.xx)	xx.x (xx.xx)	xx.x (xx.xx)
Median	xx.x	xx.x	xx.x	xx.x
Q1, Q3	xx.x, xx.x	xx.x, xx.x	xx.x, xx.x	xx.x, xx.x
Min, Max	xx, xx	xx, xx	xx, xx	xx, xx
Day 5				
n	xx	xx	xx	xx
Mean (SE)	xx.x (xx.xx)	xx.x (xx.xx)	xx.x (xx.xx)	xx.x (xx.xx)
Median	xx.x	xx.x	xx.x	xx.x
Q1, Q3	xx.x, xx.x	xx.x, xx.x	xx.x, xx.x	xx.x, xx.x
Min, Max	xx, xx	xx, xx	xx, xx	xx, xx
Day 7				
n	xx	xx	xx	xx
Mean (SE)	xx.x (xx.xx)	xx.x (xx.xx)	xx.x (xx.xx)	xx.x (xx.xx)
Median	xx.x	xx.x	xx.x	xx.x
Q1, Q3	xx.x, xx.x	xx.x, xx.x	xx.x, xx.x	xx.x, xx.x
Min, Max	xx, xx	xx, xx	xx, xx	xx, xx
Source: Listing 16.x.x.x				

Clear Creek Bio, Inc.: Protocol CCB-CRISIS-01

Table 14.3.1.1

Overall Summary of Treatment-Emergent Adverse Events by Treatment
Modified Intent-to-Treat Population

	SOC + Brequinar (N=xx) n (%)	SOC (N=xx) n (%)	Total (N=xx) n (%)
Subjects with 1 or more TEAE	xx (xx.x)	xx (xx.x)	xx (xx.x)
Subjects with 1 or more treatment-related ^a TEAE	xx (xx.x)	xx (xx.x)	xx (xx.x)
Subjects with 1 or more Grade 3 or above TEAE	xx (xx.x)	xx (xx.x)	xx (xx.x)
Subjects with 1 or more TEAE leading to drug withdrawn	xx (xx.x)	xx (xx.x)	xx (xx.x)
Subjects with 1 or more TEAE leading to study discontinuation	xx (xx.x)	xx (xx.x)	xx (xx.x)
Subjects with 1 or more serious TEAE	xx (xx.x)	xx (xx.x)	xx (xx.x)
Subjects with fatal TEAE	xx (xx.x)	xx (xx.x)	xx (xx.x)
Subjects with TEAE of interest	xx (xx.x)	xx (xx.x)	xx (xx.x)
Total number of TEAEs	xx	xx	xx
Total number of study drug-related ^a TEAEs	xx	xx	xx
Total number of Grade 3 or above TEAEs	xx	xx	xx
Total number of TEAEs leading to drug withdrawn	xx	xx	xx
Total number of TEAEs leading to study discontinuation	xx	xx	xx
Total number of serious TEAEs	xx	xx	xx
Total number of TEAEs of interest	xx	xx	xx

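### The half-LLOQ rule makes Table 14.2.8 print 2.5 mcg/mL of brequinar for SOC and pre-dose samples, and understates brequinar-arm changes to quantifiable levels by 2.5 mcg/mL

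*SAP*

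**What the plan says.** SAP Section 3.3 gives one rule for both DHO and brequinar: "samples below the lower limit of quantitation (LLOQ) will be set to half of the LLOQ value for the summary tables". It adds that the "LLOQ of concentration level is 5 mcg/mL". It does not separate pre-dose from post-dose samples, or one arm from the other.

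Section 1.2 gives the drug to one arm only: "In addition to SOC, the brequinar group will receive brequinar 100 mg once daily for 5 days". Section 1.2.1 plans "approximately 8 subjects assigned to SOC alone and approximately 16 subjects on SOC plus brequinar". For brequinar concentration, Section 3.1 applies the general definition, "Baseline will be the last non-missing value prior to randomization, including unscheduled assessments", which puts Baseline before any dose.

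Section 2.5.3 states "Changes from baseline will be summarized by treatment" and lists "Brequinar concentration levels (Days 3, 5 and 7"). The shell for Table 14.2.8, titled "Summary of Change from Baseline in Brequinar Concentration Level (mcg/mL"), has a Baseline row and rows for Days 3, 5 and 7. Each arm, SOC included, has a Visit column and a Change from Baseline column. The shell for Listing 16.2.5.2 also provides for PK results in SOC subjects, and its example SOC subject has a Day 1 result flagged as below the limit of 5.

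**The concern.** Half the LLOQ stands in for a value known only to lie between 0 and the LLOQ. That is reasonable for DHO, a metabolite the body makes itself, and for brequinar after dosing. It does not suit a brequinar sample taken before the first dose or from an SOC subject, because there the design fixes the level at 0. Section 3.3 already uses 0 in a comparable case: SARS-CoV-2 that is not detected is set to 0.

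Followed as written, the only planned summary table of brequinar concentration would show drug in people who had received none. It would also subtract that artificial level from the on-treatment values of treated subjects whenever a change is formed.

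**Working it through.** **Inputs.** LLOQ = 5 mcg/mL (Section 3.3). Arms of about 8 SOC and about 16 SOC + brequinar (Section 1.2.1). Baseline before randomization (Section 3.1). Assumption: the true level is 0 in every pre-dose sample and every SOC sample, and all of these are reported below the LLOQ.

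**Substituted value.** The SAP does not print it, but it follows directly: 5 / 2 = 2.5 mcg/mL.

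**SOC arm.** All 8 values are 2.5 at each visit, so mean, median, minimum and maximum are 2.5 and SE = 0. Change = 2.5 − 2.5 = 0, which equals the true change.

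**Brequinar arm, Baseline.** The table shows 2.5; the true value is 0.

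**Brequinar arm, post-dose.** Let C be the true level, taking a quantifiable measurement as C.

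- If C ≥ 5: table change = C − 2.5; true change = C − 0 = C; understatement = 2.5.
- If C < 5: table change = 2.5 − 2.5 = 0; true change = C; understatement = C, from 0 to just under 5.

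The SAP gives no expected concentrations, so these levels are illustrative:

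| C (mcg/mL) | Visit column | Table change | True change | Understated by |
|---|---|---|---|---|
| 1 | 2.5 | 0 | 1 | 1 (100%) |
| 4 | 2.5 | 0 | 4 | 4 (100%) |
| 5 | 5 | 2.5 | 5 | 2.5 (50%) |
| 10 | 10 | 7.5 | 10 | 2.5 (25%) |
| 20 | 20 | 17.5 | 20 | 2.5 (12.5%) |
| 30 | 30 | 27.5 | 30 | 2.5 (8.3%) |

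**Mean change in the brequinar arm.** With k of 16 post-dose samples quantifiable, the mean understatement lies between k × 2.5 / 16 and [k × 2.5 + (16 − k) × 5] / 16, the upper end being approached but not reached when k < 16.

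- k = 16: 2.5.
- k = 8: 20 / 16 = 1.25 to 60 / 16 = 3.75.
- k = 0: 0 to 5.

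**With pre-dose and SOC results set to 0.** The SOC visit means and the brequinar-arm Baseline become 0, and a change to a quantifiable level becomes C. A post-dose sample still set to 2.5 would show a change of 2.5 − 0 = +2.5 whatever its true level, so the change columns would carry a new artefact if they were kept.

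**The case against.** The strongest reply is that little depends on this. Brequinar concentration is an exploratory objective with no test and no decision rule. The trial is open label, so a constant 2.5 with SE 0 in the SOC column would be recognised as half the stated LLOQ. The substitution applies to summary tables only, and Listing 16.2.5.2 keeps the below-limit flag. All of this stands and keeps the point small. It does not make the printed values right.

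A reader might infer three stronger things that the SAP does not support:

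- *That every change from baseline is understated by 2.5 mcg/mL.* It is not. SOC changes are correctly 0, and for a post-dose sample below the LLOQ the error is the unknown true level. The figure of 2.5 is exact only for brequinar-arm changes from a baseline below the LLOQ to a quantifiable level.
- *That exposure in treated subjects is biased downward throughout.* The Visit column shows each quantifiable sample as measured. For a post-dose sample below the LLOQ, the Visit value of 2.5 may be too high or too low.
- *That an analysis relating DHO or viral load to drug level would inherit the error.* Section 2.5.3 plans descriptive summaries only, and the individual values in the listing are not substituted.

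It can also be said that restricting the table to the brequinar arm and dropping the change columns removes most of the problem without a new rule. That is largely right. The new rule is still needed for the Baseline row, and it settles the matter for any other summary.

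**Conclusion.** The point holds within limits. As written, Section 3.3 together with Table 14.2.8 reports 2.5 mcg/mL for SOC subjects at every visit and for the brequinar arm at Baseline, and understates by 2.5 mcg/mL each brequinar-arm change from a baseline below the LLOQ to a quantifiable level. This is a stated rule that gives wrong values, not a missing detail.

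The conclusion assumes that pre-dose and SOC samples contain no brequinar and are reported below the LLOQ. The relative size depends on on-treatment levels, which the SAP does not give. The mean effect depends on the share of post-dose samples above 5 mcg/mL, also not given, hence the ranges above. The effect is limited to one exploratory descriptive table and touches neither the primary safety objective nor any secondary analysis.

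**What to change.** In Section 3.3, treat brequinar separately from DHO:

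- Set brequinar results below the LLOQ to 0 for all pre-dose samples and all SOC samples.
- Keep half the LLOQ only for post-dose samples in the brequinar arm, and show n (%) below the LLOQ at each visit.
- Leave the DHO rule as it is.

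Make Table 14.2.8 a summary of concentration by visit for SOC + Brequinar only, without the change-from-baseline columns, and amend the brequinar line in Section 2.5.3 to match. Dropping those columns matters because the mixed substitution would otherwise give each post-dose sample below the LLOQ an artificial change of +2.5. SOC results remain visible in Listing 16.2.5.2.

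The cost is a sentence in Section 3.3, a matching edit in Section 2.5.3 and a simpler shell. No new data are needed and no other endpoint changes.

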4. CHANGES FROM THE PROTOCOL

Plasma viral load was listed in the protocol (Section 11.3) but will not be collected.

Nasopharyngeal viral culture was not listed in the protocol but was added to the central laboratory assessments.

The mITT population was not included in the protocol, but will be used for all analyses instead of the ITT population.

Confidential Document

	CCB-CRISIS-01 Statistical Analysis Plan	Revision No. 1.0
	Document Date: 17-Dec-2020	Page 15 of 17

APPENDIX 1 CTCAE V4.03 GRADING FOR LABORATORY VALUES

Lab Test	Lab Unit	Grade 1	Grade 2	Grade 3	Grade 4
Albumin	G/DL	3 to <LLN	2 to <3	<2	Clinical Review Needed: Life-threatening consequences; urgent intervention indicated
Alkaline Phosphatase	U/L	>ULN to 2.5xULN	>2.5xULN to 5xULN	>5xULN to 20xULN	>20xULN
Alanine Amino Transferase	U/L	>ULN to 3xULN	>3xULN to 5xULN	>5xULN to 20xULN	>20xULN
Aspartate Amino Transferase	U/L	>ULN to 2.5xULN	>2.5xULN to 5xULN	>5xULN to 20xULN	>20xULN
Bilirubin Total	MG/DL	>ULN to 1.5xULN	>1.5xULN to 3xULN	>3xULN to 10xULN	>10xULN
Calcium	MG/DL	>ULN to 11.5	>11.5 to 12.5	>12.5 to 13.5	>13.5
Calcium	MG/DL	8 to <LLN	7 to <8	6 to <7	<6
Creatinine	MG/DL	>ULN to 1.5xULN	>1.5xULN to 3xULN	>3xULN to 6xULN	>6xULN
Glucose	MG/DL	>ULN to 160	>160 to 250	>250 to 500	>500
Glucose	MG/DL	55 to <LLN	40 to <55	30 to <40	<30
Potassium	MMOL/L	>ULN to 5.5	>5.5 to 6	>6 to 7	>7

Confidential Document

Lab Test	Lab Unit	Grade 1	Grade 2	Grade 3	Grade 4
Potassium	MMOL/L	Clinical Review Needed: Check Grade 2 and reassign if not symptomatic and no intervention indicated	3 to <LLN	2.5 to <3	<2.5
Sodium	MMOL/L	>ULN to 150	>150 to 155	>155 to 160	>160
Sodium	MMOL/L	130 to <LLN	-	120 to <130	<120
Lymphocytes, Absolute	10 ³ /UL	-	>4 to 20	>20	-
Lymphocytes, Absolute	10 ³ /UL	0.8 to <LLN	0.5 to <0.8	0.2 to <0.5	<0.2
Neutrophils, Absolute	10 ³ /UL	-	-	<1	Clinical Review Needed: Life-threatening consequences; urgent intervention indicated
Neutrophils, Absolute	10 ³ /UL	1.5 to <LLN	1 to <1.5	0.5 to <1	<0.5
Hemoglobin	G/DL	>0 to 2	>2 to 4	>4	
Hemoglobin	G/DL	>ULN to ULN+2	>ULN+2 to ULN+4	>ULN+4	
Hemoglobin	G/DL	10 to <LLN	8 to <10	<8	Clinical Review Needed: Life-threatening consequences; urgent intervention indicated
Platelet Count	10 ³ /UL	75 to <LLN	50 to <75	25 to <50	<25

Confidential Document

	CCB-CRISIS-01 Statistical Analysis Plan	Revision No. 1.0
	Document Date: 17-Dec-2020	Page 17 of 17

Lab Test	Lab Unit	Grade 1	Grade 2	Grade 3	Grade 4
White Blood Cell	10 ³ /UL	-	-	>100	Clinical Review Needed: Clinical manifestations of leucostasis; urgent intervention indicated
White Blood Cell	10 ³ /UL	3 to <LLN	2 to <3	1 to <2	<1

Note: For these laboratory tests, Grade 0 is assigned if result does not meet above ranges.

Confidential Document

**CLEAR CREEK BIO. INC.
PROPOSED TABLES and LISTINGS
PROTOCOL CCB-CRISIS-01**

**Version 1.0
17-Dec-2020**

[figure not shown]

**CLEAR CREEK BIO. INC.
PROPOSED TABLES and LISTINGS
PROTOCOL CCB-CRISIS-01**

**Version 1.0
17-Dec-2020**

Signature Page

The proposed tables and listings have been reviewed and approved by the following personnel:

Prosoft Personnel

Title	Printed Name	Signature	Date
Manager, Statistics	[name]	 DocuSigned by: [name]	17-Dec-2020
Associate Vice President, Statistics	[name]	 DocuSigned by: Signer Name: [name] Signing Reason: I have reviewed this document Signing Time: 17-Dec-2020 1:30:59 PM PST	17-Dec-2020

CCB Personnel

Title	Printed Name	Signature	Date
Vice President, Clinical Operations	[name]	 DocuSigned by: Signer Name: [name] Signing Reason: I approve this document Signing Time: 17-Dec-2020 1:40:07 PM PST 57DEAAD17C2240FEA72C57ABA124E827	17-Dec-2020

CLEAR CREEK BIO. INC.
PROPOSED TABLES and LISTINGS
PROTOCOL CCB-CRISIS-01

TABLES

BOLD = SAMPLE IS PROVIDED.

Table 14.1.1	Summary of Population by Site and Treatment
Table 14.1.2	Summary of Subject Disposition by Site and Treatment (Modified Intent-to-Treat Population)
Table 14.1.3	Summary of Demographics and Baseline Characteristics by Treatment (Modified Intent-to-Treat Population)
Table 14.1.4	Summary of Medical History by Treatment (Modified Intent-to-Treat Population)
Table 14.1.5.1	Summary of Prior Medications by Treatment (Modified Intent-to-Treat Population)
Table 14.1.5.2	Summary of Concomitant Medications by Treatment (Modified Intent-to-Treat Population)
Table 14.1.6.1	Summary of Prior Procedures by Treatment (Modified Intent-to-Treat Population)
Table 14.1.6.2	Summary of Concomitant Procedures by Treatment (Modified Intent-to-Treat Population)
Table 14.2.1	Summary of Hospitalization Status and Mortality Rate by Treatment and Visit (Modified Intent-to-Treat Population)
Table 14.2.2.1	Summary of Kaplan Meier Estimates for Duration of Hospitalization by Treatment (Modified Intent-to-Treat Population)
Figure 14.2.2.2	Duration of Hospitalization by Treatment (Modified Intent-to-Treat Population)
Table 14.2.3.1	Summary of Kaplan Meier Estimates for Time to Death by Treatment (Modified Intent-to-Treat Population)
Figure 14.2.3.2	Time to Death by Treatment (Modified Intent-to-Treat Population)
Table 14.2.4.1	Summary of NEWS2 Scores by Treatment and Visit (Modified Intent-to-Treat Population)
Table 14.2.4.2	Summary of NEWS2 Parameters by Treatment and Visit (Modified Intent-to-Treat Population)
Table 14.2.5	Summary of Change from Baseline in SARS-CoV-2 Viral Load (copies/mL) by Treatment and Visit (Modified Intent-to-Treat Population)
Table 14.2.6	Summary of Change from Baseline in Inflammatory Markers by Treatment and Visit (Modified Intent-to-Treat Population)
Table 14.2.7	Summary of Change from Baseline in DHO Level (ng/mL) by Treatment and Visit (Modified Intent-to-Treat Population)

Table 14.2.8	Summary of Change from Baseline in Brequinar Concentration Level (mcg/mL) by Treatment and Visit (Modified Intent-to-Treat Population)
Table 14.3.1.1	Overall Summary of Treatment-Emergent Adverse Events by Treatment (Modified Intent-to-Treat Population)
Table 14.3.1.2	Summary of Treatment-Emergent Adverse Events by Treatment (Modified Intent-to-Treat Population)
Table 14.3.1.3	Summary of Related Treatment-Emergent Adverse Events by Treatment (Modified Intent-to-Treat Population)
Table 14.3.1.4	Summary of Serious Treatment-Emergent Adverse Events by Treatment (Modified Intent-to-Treat Population)
Table 14.3.1.5	Summary of Treatment-Emergent Adverse Events Leading to Study Discontinuation by Treatment (Modified Intent-to-Treat Population)
Table 14.3.1.6	Summary of Treatment-Emergent Adverse Events of Interest by Treatment (Modified Intent-to-Treat Population)
Table 14.3.1.7	Summary of Treatment-Emergent Adverse Events by Severity and Treatment (Modified Intent-to-Treat Population)
Table 14.3.2	Summary of Change from Baseline in Laboratory Parameters of Special Interest by Treatment and Visit (Modified Intent-to-Treat Population)

LISTINGS

Listing 16.2.1	Listing of End of Study Status by Treatment
Listing 16.2.2	Listing of Inclusion/Exclusion Criteria and Randomization
Listing 16.2.3	Listing of Informed Consent and Study Populations by Treatment
Listing 16.2.4.1	Listing of Subject Demographics by Treatment
Listing 16.2.4.2	Listing of Medical History by Treatment
Listing 16.2.4.3	Listing of Prior and Concomitant Medications by Treatment
Listing 16.2.4.4	Listing of Prior and Concomitant Procedures by Treatment
Listing 16.2.5.1	Listing of Dosing Information (SOC + Brequinar Only)
Listing 16.2.5.2	Listing of PK/DHO Results by Treatment
Listing 16.2.6.1	Listing of NEWS2 Assessments by Treatment
Listing 16.2.6.2	Listing of Inflammatory Markers by Treatment
Listing 16.2.6.3	Listing of SARS-CoV-2 Viral Load and Viral Culture by Treatment
Listing 16.2.6.4	Listing of Hospitalization Log by Treatment
Listing 16.2.6.5	Listing of Survival Status by Treatment
Listing 16.2.7.1	Listing of Adverse Events by Treatment
Listing 16.2.7.2	Listing of Related Adverse Events by Treatment
Listing 16.2.7.3	Listing of Serious Adverse Events by Treatment
Listing 16.2.7.4	Listing of Grade 3 or 4 Adverse Events by Treatment
Listing 16.2.8.1.1	Listing of Chemistry Laboratory Tests by Treatment
Listing 16.2.8.1.2	Listing of Grade 3 or 4 Chemistry Laboratory Tests by Parameter and Treatment
Listing 16.2.8.2.1	Listing of Hematology Laboratory Tests by Treatment
Listing 16.2.8.2.2	Listing of Grade 3 or 4 Hematology Laboratory Tests by Parameter and Treatment
Listing 16.2.8.3	Listing of Urinalysis Laboratory Tests by Treatment

Conventions:

- For categorical data:
 - Percents are displayed with one decimal
 - When displaying counts and percents, the percent is contained within parentheses and does not include the “%” symbol
 - If the count is zero, no percent is displayed
 - If missing data occurs, a “Missing” row will be added to the summary table. The count of missing will be presented (no percent). The percentages for remaining rows will be based on the number of non-missing responses (i.e., the denominator does not include the missing counts)
- For continuous data, rounding will be based on the following conventions unless otherwise specified
 - Min and Max displayed to the same number of decimals as the original data
 - Mean, Median, and other percentiles displayed to 1 more decimal than the original data
 - SE and CIs displayed to 2 more decimals than the original data

Clear Creek Bio, Inc.: Protocol CCB-CRISIS-01

Table 14.1.1

Summary of Populations by Site and Treatment

	SOC + Brequinar n (%)	SOC n (%)
Overall		
Randomized	xx	xx
Modified Intent-to-Treat ^a	xx (xx.x)	xx (xx.x)
Site xx		
Randomized	xx	xx
Modified Intent-to-Treat ^a	xx (xx.x)	xx (xx.x)
a: Modified Intent-to-Treat (mITT) population includes all randomized subjects who had at least one post-randomization assessment, and who received at least one dose of study medication if randomized to SOC + Brequinar group. Source: Listing 16.X.X.X		

Clear Creek Bio, Inc.: Protocol CCB-CRISIS-01
 Table 14.1.2
 Summary of Subject Disposition by Site and Treatment
 Modified Intent-to-Treat Population

	SOC + Brequinar (N=xx) n (%)	SOC (N=xx) n (%)
Overall		
Completed the study (through Day 15)	xx (xx.x)	xx (xx.x)
Discontinued	xx (xx.x)	xx (xx.x)
Physician Decision	xx (xx.x)	xx (xx.x)
Adverse Event	xx (xx.x)	xx (xx.x)
Withdrawal by Subject	xx (xx.x)	xx (xx.x)
Study Terminated by Sponsor	xx (xx.x)	xx (xx.x)
Protocol Violation	xx (xx.x)	xx (xx.x)
Lost to Follow-Up	xx (xx.x)	xx (xx.x)
Other	xx (xx.x)	xx (xx.x)
Site xx		
Completed the study (through Day 15)	xx (xx.x)	xx (xx.x)
Discontinued	xx (xx.x)	xx (xx.x)
Physician Decision	xx (xx.x)	xx (xx.x)
Adverse Event	xx (xx.x)	xx (xx.x)
Withdrawal by Subject	xx (xx.x)	xx (xx.x)
Study Terminated by Sponsor	xx (xx.x)	xx (xx.x)
Protocol Violation	xx (xx.x)	xx (xx.x)
Lost to Follow-Up	xx (xx.x)	xx (xx.x)
Other	xx (xx.x)	xx (xx.x)
Source: Listing 16.X.X.X		

Programming note: Sort in descending frequency based on the number of subjects in the SOC + Brequinar group, except for “Other” that shall stay at the last row. Sort alphabetically to break ties.

Clear Creek Bio, Inc.: Protocol CCB-CRISIS-01

Table 14.1.3

Summary of Demographics and Baseline Characteristics by Treatment
Modified Intent-to-Treat Population

Parameter	SOC + Brequinar (N=xx)	SOC (N=xx)
Age (years)		
n	xx	xx
Mean (SE)	xx.x (xx.xx)	xx.x (xx.xx)
Median	xx.x	xx.x
Q1, Q3	xx.x, xx.x	xx.x, xx.x
Min, Max	xx, xx	xx, xx
Sex, [n (%)]		
Male	xx (xx.x)	xx (xx.x)
Female	xx (xx.x)	xx (xx.x)
Ethnicity, [n (%)]		
Hispanic or Latino	xx (xx.x)	xx (xx.x)
Not Hispanic or Latino	xx (xx.x)	xx (xx.x)
Race, [n (%)]		
White	xx (xx.x)	xx (xx.x)
Black or African American	xx (xx.x)	xx (xx.x)
Asian	xx (xx.x)	xx (xx.x)
American Indian or Alaska Native	xx (xx.x)	xx (xx.x)
Native Hawaiian or Other Pacific Islander	xx (xx.x)	xx (xx.x)
Other	xx (xx.x)	xx (xx.x)
Height (cm)		
n	xx	xx
Mean (SE)	xx.x (xx.xx)	xx.x (xx.xx)
Median	xx.x	xx.x
Q1, Q3	xx.x, xx.x	xx.x, xx.x
Min, Max	xx, xx	xx, xx
Weight (kg)		
n	xx	xx
Mean (SE)	xx.x (xx.xx)	xx.x (xx.xx)
Median	xx.x	xx.x
Q1, Q3	xx.x, xx.x	xx.x, xx.x
Min, Max	xx, xx	xx, xx
BSA (m2)		
n	xx	xx
Mean (SE)	xx.x (xx.xx)	xx.x (xx.xx)
Median	xx.x	xx.x
Q1, Q3	xx.x, xx.x	xx.x, xx.x
Min, Max	xx, xx	xx, xx
Source: Listing 16.X.X.X		

Clear Creek Bio, Inc.: Protocol CCB-CRISIS-01

Table 14.1.3

Summary of Demographics and Baseline Characteristics by Treatment

Intent-to-Treat Population

Parameter	SOC + Brequinar (N=xx)	SOC (N=xx)
NEWS2 Score		
n	xx	xx
Mean (SE)	xx.x (xx.xx)	xx.x (xx.xx)
Median	xx.x	xx.x
Q1, Q3	xx.x, xx.x	xx.x, xx.x
Min, Max	xx, xx	xx, xx
ICU Level of Care at Randomization, [n (%)]		
Yes	xx (xx.x)	xx (xx.x)
No	xx (xx.x)	xx (xx.x)
Source: Listing 16.X.X.X		

Clear Creek Bio, Inc.: Protocol CCB-CRISIS-01

Table 14.1.4

Summary of Medical History by Treatment

Modified Intent-to-Treat Population

System Organ Class Preferred Term	SOC+ Brequinar (N=xx) n (%)	SOC (N=xx) n (%)
Any Medical History Event		
Overall	xx (xx.x)	xx (xx.x)
SOC 1		
Overall	xx (xx.x)	xx (xx.x)
Preferred Term 1	xx (xx.x)	xx (xx.x)
Preferred Term 2	xx (xx.x)	xx (xx.x)
SOC 2		
Overall	xx (xx.x)	xx (xx.x)
Preferred Term 1	xx (xx.x)	xx (xx.x)
Preferred Term 2	xx (xx.x)	xx (xx.x)
etc.		
Note: Subjects reporting multiple occurrences of the same preferred term are only counted once within a given cell. Source: Listing 16.X.X.X		

Programming note: Sort in descending frequency based on the number of subjects in the SOC+ Brequinar group.
Sort alphabetically to break ties.

Clear Creek Bio, Inc.: Protocol CCB-CRISIS-01

Table 14.1.5.1

Summary of Prior Medications by Treatment
Modified Intent-to-Treat Population

Pharmacological Subgroup Prior Medication	SOC+ Brequinar (N=xx) n (%)	SOC (N=xx) n (%)
Any Prior Medication		
Overall	xx (xx.x)	xx (xx.x)
Subgroup 1		
Overall	xx (xx.x)	xx (xx.x)
Medication 1	xx (xx.x)	xx (xx.x)
Medication 2	xx (xx.x)	xx (xx.x)
Subgroup 2		
Overall	xx (xx.x)	xx (xx.x)
Medication 1	xx (xx.x)	xx (xx.x)
Medication 2	xx (xx.x)	xx (xx.x)
etc.		
Note: Subjects reporting multiple medications of the same coded term are only counted once within a given cell. Source: Listing 16.X.X.X		

Programming note: Sort medications in descending frequency based on the number of subjects in the SOC + Brequinar group. Sort alphabetically to break ties. Pharmacological Subgroup comes from ATC3. If ATC3 is not available, use ATC2

Change column header to “System Organ Class Preferred Term” for Procedure tables.

Clear Creek Bio, Inc.: Protocol CCB-CRISIS-01

Table 14.2.1

Summary of Hospitalization Status and Mortality Rate by Treatment and Visit
 Modified Intent-to-Treat Population

Study Day Hospitalization Status	SOC + Brequinar (N=xx) n (%)	SOC (N=xx) n (%)
Study Day 3		
Died	xx (xx.x)	xx (xx.x)
Hospitalized in ICU	xx (xx.x)	xx (xx.x)
Initial Hospitalization	xx (xx.x)	xx (xx.x)
Re-Hospitalization	xx (xx.x)	xx (xx.x)
Hospitalized (not ICU)	xx (xx.x)	xx (xx.x)
Initial Hospitalization	xx (xx.x)	xx (xx.x)
Re-Hospitalization	xx (xx.x)	xx (xx.x)
Discharged	xx (xx.x)	xx (xx.x)
Initial Hospitalization	xx (xx.x)	xx (xx.x)
Re-Hospitalization	xx (xx.x)	xx (xx.x)
Missing	xx	xx
etc.		
Study Day 15		
Died	xx (xx.x)	xx (xx.x)
Hospitalized in ICU	xx (xx.x)	xx (xx.x)
Initial Hospitalization	xx (xx.x)	xx (xx.x)
Re-Hospitalization	xx (xx.x)	xx (xx.x)
Hospitalized (not ICU)	xx (xx.x)	xx (xx.x)
Initial Hospitalization	xx (xx.x)	xx (xx.x)
Re-Hospitalization	xx (xx.x)	xx (xx.x)
Discharged	xx (xx.x)	xx (xx.x)
Initial Hospitalization	xx (xx.x)	xx (xx.x)
Re-Hospitalization	xx (xx.x)	xx (xx.x)
Missing	xx	xx
Day 29 Contact		
Died	xx (xx.x)	xx (xx.x)
Alive	xx (xx.x)	xx (xx.x)
Missing	xx	xx
Source: Listing 16.x.x.x		

Programming notes: summarize hospitalization status and death on Study Day 3, 5, 7, 15; summarize only death on Day 29. Include missing rows to capture unknown status.

Clear Creek Bio, Inc.: Protocol CCB-CRISIS-01

Table 14.2.2.1

Summary of Kaplan Meier Estimates for Duration of Hospitalization by Treatment
Modified Intent-to-Treat Population

	SOC + Brequinar (N=xx)	SOC (N=xx)
Total Patients Discharged	xx	xx
Number of Censored ^a	xx	xx
Not Discharged by Day 15 Visit	xx	xx
Did Not Complete Study	xx	xx
Q1	xx	xx
Median	xx	xx
Q3	xx	xx
Note: Duration of hospitalization is defined as Study Day at time of initial discharge. a: Subjects who were not discharged by the Day 15 visit will be censored at the Day 15 visit. Subjects who did not complete the trial while still hospitalized will be censored at the date of last contact. Source: Listing 16.x.x.x		

Clear Creek Bio, Inc.: Protocol CCB-CRISIS-01
Figure 14.2.2.2
Duration of Hospitalization by Treatment
Modified Intent-to-Treat Population

Note: Duration of hospitalization is defined as the Study Day at time of initial discharge. Subjects who were not discharged by the Day 15 visit will be censored at the Day 15 visit. Subjects who did not complete the trial while still hospitalized will be censored at the date of last contact.
Source: 16.x.x.x

Clear Creek Bio, Inc.: Protocol CCB-CRISIS-01

Table 14.2.3.1

Summary of Kaplan Meier Estimates for Time to Death by Treatment
Modified Intent-to-Treat Population

	SOC + Brequinar (N=xx)	SOC (N=xx)
Number of Deaths	xx	xx
Number of Censored ^a	xx	xx
Alive at Day 29 Contact	xx	xx
Unknown	xx	xx
Q1	xx	xx
Median	xx	xx
Q3	xx	xx
a: Subjects who are alive at the Day 29 contact will be censored at the Day 29 contact. Subjects whose Day 29 survival is unknown will be censored at the date of last contact. Source: Listing 16.x.x.x		

Clear Creek Bio., Inc.: Protocol CCB-CRISIS-01
Figure 14.2.3.2
Time to Death by Treatment
Intent-to-Treat Population

Note: Subjects who are alive at the Day 29 contact will be censored at the Day 29 contact. Subjects whose Day 29 survival is unknown will be censored at the date of last contact.
Source: 16.x.x.x

Clear Creek Bio., Inc.: Protocol CCB-CRISIS-01

Table 14.2.4.1

Summary of NEWS2 Scores by Treatment and Visit
Modified Intent-to-Treat Population

Visit	SOC + Brequinar (N=xx)		SOC (N=xx)	
	Visit	Change from Baseline	Visit	Change from Baseline
Baseline				
n	xx		xx	
Mean (SE)	xx.x (xx.xx)		xx.x (xx.xx)	
Median	xx.x		xx.x	
Q1, Q3	xx.x, xx.x		xx.x, xx.x	
Min, Max	xx, xx		xx, xx	
0-4	xx (xx.x)		xx (xx.x)	
5-6	xx (xx.x)		xx (xx.x)	
7 or Higher	xx (xx.x)		xx (xx.x)	
Day 3				
n	xx	xx	xx	xx
Mean (SE)	xx.x (xx.xx)	xx.x (xx.xx)	xx.x (xx.xx)	xx.x (xx.xx)
Median	xx.x	xx.x	xx.x	xx.x
Q1, Q3	xx.x, xx.x	xx.x, xx.x	xx.x, xx.x	xx.x, xx.x
Min, Max	xx, xx	xx, xx	xx, xx	xx, xx
0-4	xx (xx.x)		xx (xx.x)	
5-6	xx (xx.x)		xx (xx.x)	
7 or Higher	xx (xx.x)		xx (xx.x)	
etc.				
Source: Listing 16.x.x.x				

Programming note: Include Day 3, 5, 7, 15.

Clear Creek Bio, Inc.: Protocol CCB-CRISIS-01

Table 14.2.4.2

Summary of NEWS2 Parameters by Treatment and Visit
Modified Intent-to-Treat Population

Parameter Visit	SOC + Brequinar (N=xx)		SOC (N=xx)	
	Visit	Change from Baseline	Visit	Change from Baseline
Systolic Blood Pressure (mmHg)				
Baseline				
n	xx		xx	
Mean (SE)	xx.x (xx.xx)		xx.x (xx.xx)	
Median	xx.x		xx.x	
Q1, Q3	xx.x, xx.x		xx.x, xx.x	
Min, Max	xx, xx		xx, xx	
Day 3				
n	xx	xx	xx	xx
Mean (SE)	xx.x (xx.xx)	xx.x (xx.xx)	xx.x (xx.xx)	xx.x (xx.xx)
Median	xx.x	xx.x	xx.x	xx.x
Q1, Q3	xx.x, xx.x	xx.x, xx.x	xx.x, xx.x	xx.x, xx.x
Min, Max	xx, xx	xx, xx	xx, xx	xx, xx
...				
Supplemental Oxygen				
Baseline				
Subject with value	xx		xx	
Yes, [n (%)]	xx (xx.x)		xx (xx.x)	
No, [n (%)]	xx (xx.x)		xx (xx.x)	
...				
Hypercapnic Respiratory Failure				
Baseline				
Subject with value	xx		xx	
Yes, [n (%)]	xx (xx.x)		xx (xx.x)	
No, [n (%)]	xx (xx.x)		xx (xx.x)	
Unknown, [n (%)]	xx (xx.x)		xx (xx.x)	
etc.				
Note: Percentages of Supplemental Oxygen, Hypercapnic Respiratory Failure and Level of Consciousness Alert are based on the Subject with value.				
Source: Listing 16.x.x.x				

Programming notes: summarize all NEWS2 parameters on Day 3, 5, 7, 15. CFB for Oxygen, Hypercapnic and Alert won't be provided.

Clear Creek Bio, Inc.: Protocol CCB-CRISIS-01

Table 14.2.5

Summary of Change from Baseline in SARS-CoV-2 Viral Load (copies/mL) by Treatment and Visit
Modified Intent-to-Treat Population

Visit	SOC + Brequinar (N=xx)		SOC (N=xx)	
	Visit	Change from Baseline	Visit	Change from Baseline
Baseline				
n	xx		xx	
Mean (SE)	xx.x (xx.xx)		xx.x (xx.xx)	
Median	xx.x		xx.x	
Q1, Q3	xx.x, xx.x		xx.x, xx.x	
Min, Max	xx, xx		xx, xx	
Day 3				
n	xx	xx	xx	xx
Mean (SE)	xx.x (xx.xx)	xx.x (xx.xx)	xx.x (xx.xx)	xx.x (xx.xx)
Median	xx.x	xx.x	xx.x	xx.x
Q1, Q3	xx.x, xx.x	xx.x, xx.x	xx.x, xx.x	xx.x, xx.x
Min, Max	xx, xx	xx, xx	xx, xx	xx, xx
Day 5				
n	xx	xx	xx	xx
Mean (SE)	xx.x (xx.xx)	xx.x (xx.xx)	xx.x (xx.xx)	xx.x (xx.xx)
Median	xx.x	xx.x	xx.x	xx.x
Q1, Q3	xx.x, xx.x	xx.x, xx.x	xx.x, xx.x	xx.x, xx.x
Min, Max	xx, xx	xx, xx	xx, xx	xx, xx
etc.				
Source: Listing 16.2.x				

Programming note: Include Day 3,5,7,15.

Clear Creek Bio, Inc.: Protocol CCB-CRISIS-01

Table 14.2.6

Summary of Change from Baseline in Inflammatory Markers by Treatment and Visit
 Modified Intent-to-Treat Population

Parameter Visit	SOC + Brequinar (N=xx)		SOC (N=xx)	
	Visit	Change from Baseline	Visit	Change from Baseline
Parameter 1 (unit), Normal Range=xx-xx Baseline				
n	xx		xx	
Mean (SE)	xx.x (xx.xx)		xx.x (xx.xx)	
Median	xx.x		xx.x	
Q1, Q3	xx.x, xx.x		xx.x, xx.x	
Min, Max	xx, xx		xx, xx	
Day 3				
n	xx	xx	xx	xx
Mean (SE)	xx.x (xx.xx)	xx.x (xx.xx)	xx.x (xx.xx)	xx.x (xx.xx)
Median	xx.x	xx.x	xx.x	xx.x
Q1, Q3	xx.x, xx.x	xx.x, xx.x	xx.x, xx.x	xx.x, xx.x
Min, Max	xx, xx	xx, xx	xx, xx	xx, xx
Day 5				
n	xx	xx	xx	xx
Mean (SE)	xx.x (xx.xx)	xx.x (xx.xx)	xx.x (xx.xx)	xx.x (xx.xx)
Median	xx.x	xx.x	xx.x	xx.x
Q1, Q3	xx.x, xx.x	xx.x, xx.x	xx.x, xx.x	xx.x, xx.x
Min, Max	xx, xx	xx, xx	xx, xx	xx, xx
etc.				
Parameter 2 (unit), Normal Range=xx-xx Baseline				
Source: Listing 16.x.x.x				

Programming note: Include all parameters from local and central labs on Day 3, 5, 7, 15.

Clear Creek Bio., Inc.: Protocol CCB-CRISIS-01

Table 14.2.7

Summary of Change from Baseline in DHO Level (ng/mL) by Treatment and Visit

Intent-to-Treat Population

Visit	SOC + Brequinar (N=xx)		SOC (N=xx)	
	Visit	Change from Baseline	Visit	Change from Baseline
Baseline				
n	xx		xx	
Mean (SE)	xx.x (xx.xx)		xx.x (xx.xx)	
Median	xx.x		xx.x	
Q1, Q3	xx.x, xx.x		xx.x, xx.x	
Min, Max	xx, xx		xx, xx	
Day 3				
n	xx	xx	xx	xx
Mean (SE)	xx.x (xx.xx)	xx.x (xx.xx)	xx.x (xx.xx)	xx.x (xx.xx)
Median	xx.x	xx.x	xx.x	xx.x
Q1, Q3	xx.x, xx.x	xx.x, xx.x	xx.x, xx.x	xx.x, xx.x
Min, Max	xx, xx	xx, xx	xx, xx	xx, xx
Day 5				
n	xx	xx	xx	xx
Mean (SE)	xx.x (xx.xx)	xx.x (xx.xx)	xx.x (xx.xx)	xx.x (xx.xx)
Median	xx.x	xx.x	xx.x	xx.x
Q1, Q3	xx.x, xx.x	xx.x, xx.x	xx.x, xx.x	xx.x, xx.x
Min, Max	xx, xx	xx, xx	xx, xx	xx, xx
etc.				
Source: Listing 16.x.x.x				

Programming note: Include Day 3, 5, 7, 15.

Clear Creek Bio., Inc.: Protocol CCB-CRISIS-01

Table 14.2.8

Summary of Change from Baseline in Brequinar Concentration Level (mcg/mL)
by Treatment and Visit
Intent-to-Treat Population

Visit	SOC + Brequinar (N=xx)		SOC (N=xx)	
	Visit	Change from Baseline	Visit	Change from Baseline
Baseline				
n	xx		xx	
Mean (SE)	xx.x (xx.xx)		xx.x (xx.xx)	
Median	xx.x		xx.x	
Q1, Q3	xx.x, xx.x		xx.x, xx.x	
Min, Max	xx, xx		xx, xx	
Day 3				
n	xx	xx	xx	xx
Mean (SE)	xx.x (xx.xx)	xx.x (xx.xx)	xx.x (xx.xx)	xx.x (xx.xx)
Median	xx.x	xx.x	xx.x	xx.x
Q1, Q3	xx.x, xx.x	xx.x, xx.x	xx.x, xx.x	xx.x, xx.x
Min, Max	xx, xx	xx, xx	xx, xx	xx, xx
Day 5				
n	xx	xx	xx	xx
Mean (SE)	xx.x (xx.xx)	xx.x (xx.xx)	xx.x (xx.xx)	xx.x (xx.xx)
Median	xx.x	xx.x	xx.x	xx.x
Q1, Q3	xx.x, xx.x	xx.x, xx.x	xx.x, xx.x	xx.x, xx.x
Min, Max	xx, xx	xx, xx	xx, xx	xx, xx
Day 7				
n	xx	xx	xx	xx
Mean (SE)	xx.x (xx.xx)	xx.x (xx.xx)	xx.x (xx.xx)	xx.x (xx.xx)
Median	xx.x	xx.x	xx.x	xx.x
Q1, Q3	xx.x, xx.x	xx.x, xx.x	xx.x, xx.x	xx.x, xx.x
Min, Max	xx, xx	xx, xx	xx, xx	xx, xx
Source: Listing 16.x.x.x				

Clear Creek Bio, Inc.: Protocol CCB-CRISIS-01

Table 14.3.1.1

Overall Summary of Treatment-Emergent Adverse Events by Treatment
Modified Intent-to-Treat Population

	SOC + Brequinar (N=xx) n (%)	SOC (N=xx) n (%)	Total (N=xx) n (%)
Subjects with 1 or more TEAE	xx (xx.x)	xx (xx.x)	xx (xx.x)
Subjects with 1 or more treatment-related ^a TEAE	xx (xx.x)	xx (xx.x)	xx (xx.x)
Subjects with 1 or more Grade 3 or above TEAE	xx (xx.x)	xx (xx.x)	xx (xx.x)
Subjects with 1 or more TEAE leading to drug withdrawn	xx (xx.x)	xx (xx.x)	xx (xx.x)
Subjects with 1 or more TEAE leading to study discontinuation	xx (xx.x)	xx (xx.x)	xx (xx.x)
Subjects with 1 or more serious TEAE	xx (xx.x)	xx (xx.x)	xx (xx.x)
Subjects with fatal TEAE	xx (xx.x)	xx (xx.x)	xx (xx.x)
Subjects with TEAE of interest	xx (xx.x)	xx (xx.x)	xx (xx.x)
Total number of TEAEs	xx	xx	xx
Total number of study drug-related ^a TEAEs	xx	xx	xx
Total number of Grade 3 or above TEAEs	xx	xx	xx
Total number of TEAEs leading to drug withdrawn	xx	xx	xx
Total number of TEAEs leading to study discontinuation	xx	xx	xx
Total number of serious TEAEs	xx	xx	xx
Total number of TEAEs of interest	xx	xx	xx
